13.4 Patient Confidentiality

Patient data will be kept strictly confidential. Patient anonymity will be protected by using number codes and /or initials.

14 REPORTING AND PUBLICATION, INCLUDING ARCHIVING

The Investigator shall not divulge unpublished data or information related to the study provided by First Wave BioPharma, including but not limited to the study product characteristics, the Investigator's Brochure, the study protocol, case report forms, assay methods, or scientific data, to any third party without written approval from First Wave BioPharma. In addition, any new information that may become available during the course of the study shall be considered as confidential and shall not be used for any purpose other than the performance of the clinical study.

The study data are the property of First Wave BioPharma. The Investigator and any of the research staff shall obtain written approval from First Wave BioPharma before the publication/communication of the results of any work carried out during or in relation to the study. Publication and/or communication of the results of the clinical study will be of a cooperative nature involving authors representing First Wave BioPharma, the Investigators, and the scientific committee, if any.

First Wave BioPharma reserves the right to request modification of the content and/or timing of any publication or presentation if a patent application, an existing patent, or other proprietary rights may be jeopardized.

Authorship of any publication related to the study and the order of presentation of the authors' names shall be approved by First Wave BioPharma. First Wave BioPharma shall not use an Investigator's name in any publication without his/her written permission and vice versa.

First Wave BioPharma should retain all essential study-related documents, i.e., documents which permit evaluation of the conduct of a study and the quality of the data produced, in accordance with the applicable regulatory requirements of his/her country. These essential documents include, but are not limited to, signed protocol, Investigator's Brochure, printed CRFs, medical records, laboratory reports, informed consent forms, drug disposition records, safety reports, information regarding participants who discontinued, and other relevant documents and data.

Study-related documents should be kept together in the Investigator site file provided to the Investigator by First Wave BioPharma. Sufficient information about the identity of all study patients (e.g., name, medical records number, patient number, and study number) should be retained by the Investigator so that any First Wave BioPharma representatives, auditors, or inspectors may access this information when required. The Investigator must retain all records for 15 years or longer if required by specific local requirements. The Investigator will contact First Wave BioPharma for authorization before the destruction of any study records or in the event of accidental loss or destruction of any of them. All records should be kept in a secure area; however, in the cases of audit or inspection, they should be rapidly made available.

16.2 Clinical Laboratory Tests

Clinical Chemistry:	Hematology:
Serum Concentrations of:	Hematocrit
Sodium	Hemoglobin
Potassium	Erythrocyte count (RBC)
Chloride	Leukocytes (WBC)
Bicarbonate	Absolute counts of:
Blood urea nitrogen (BUN)	Neutrophils, segmented
Total Calcium	Neutrophils, juvenile (bands)
Phosphorus	Lymphocytes
Magnesium	Monocytes
Glucose	Eosinophils
Creatinine	Basophils
Albumin	Platelets
Prealbumin	
Total protein	Other:
Alkaline phosphatase	Serum pregnancy test ^a
Alanine aminotransferase (ALT)	Urine pregnancy test ^a
Aspartate aminotransferase (AST)	Activated partial thromboplastin time (aPTT)
Lactate dehydrogenase (LDH)	Prothrombin time/International normalized ratio (PT/INR)
Total bilirubin	
Direct bilirubin	
Uric Acid	
Fasting Lipid Profile:	Stool:
Total cholesterol	Marker-to-marker stool collection
Triglycerides	Fecal Elastase
Low Density Lipoprotein (LDL)	
High Density Lipoprotein (HDL)	
Very Low Density Lipoprotein (VLDL)	

Note: All labs will be assayed by First Wave BioPharma designated central laboratory unless otherwise noted.

a. Only for females of childbearing potential

1. LIST OF ABBREVIATIONS

Table 1: List of Abbreviations

Abbreviation	Term
AE	adverse event
ATC	Anatomical Therapeutic Chemical
BMI	body mass index
CDC	Centers for Disease Control
CF	cystic fibrosis
CFA	coefficient of fat absorption
CFF	Cystic Fibrosis Foundation
CFFT	Cystic Fibrosis Foundation Therapeutics
CFTR	cystic fibrosis transmembrane conductance regulator
CI	confidence interval(s)
CNA	coefficient of nitrogen absorption
CRF	case report form
CSR	clinical study report
EPI	exocrine pancreatic insufficiency
ICH	International Conference on Harmonisation
mITT	Modified Intent-to-treat
IP	investigational product
IR	immediate release
LS	least squares
MedDRA	Medical Dictionary for Regulatory Activities
PERT	pancreatic enzyme replacement therapy
PP	per-protocol
SAE	serious adverse event
SAP	statistical analysis plan
SD	standard deviation
SE	standard error
TEAE	treatment-emergent adverse event
U	units

First Wave BioPharma, Inc.
{Statistical Analysis Plan - Protocol #} FWB-CF-2.03

ULN	upper limit of normal
USP	United States Pharmacopeia

Page 8 of 31

Version Date: 2023-04-13

Version: 1.0

Document Control No.: TMP-SA-008-01

Template Effective Date: 23 Mar 2021

2. PURPOSE OF THE ANALYSES

The statistical analysis plan (SAP) is being developed after review of the First Wave Biopharma, Inc. (First Wave), protocol number FWB-CF-2.03 (Version 1.0), but before any analyses of the data. The SAP contains detailed information to aid in the implementation of the statistical analyses and reporting of the study data for use in the clinical study report (CSR). This SAP is being written with due consideration of the recommendations outlined in the most recent International Conference on Harmonisation (ICH) E9 Guideline entitled Guidance for Industry: Statistical Principles for Clinical Trials and the most recent ICH E3 Guideline, entitled Guidance for Industry: Structure and Content of Clinical Study Reports.

This SAP describes the analysis sets that will be analyzed, the subject characteristics parameters, the efficacy parameters, and the safety parameters that will be evaluated. The details of the specific statistical methods that will be used will be provided in this SAP. If differences occur between analyses described in the SAP and the current protocol, those found in this SAP will assume primacy. If additional analyses are required to supplement the planned analyses described in this SAP, they may be completed and will be identified in the CSR. Table and listing specifications are provided in a separate document.

3. PROTOCOL SUMMARY

3.1. Study Objectives

3.1.1. Primary Objectives

The Primary objective of this pilot study is to establish safety and efficacy of a new enteric microgranule formulation of adrulipase in patients with EPI due to CF.

The primary safety objective of this study is to assess the safety and tolerability of optimized dose of either 1.2 g/day, 1.95 g/day or 2.4 g/day of adrulipase provided in size 00 capsules containing ~150 mg adrulipase. Efficacy will be evaluated by comparing CFA values during treatment with patient-specific optimized dose of adrulipase versus baseline CFA obtained during screening of the patient's pre-study porcine PERT.

3.2. Overall Study Design and Plan

This is a Phase 2, single arm pilot study assessing the safety and efficacy of adrulipase in an enteric microgranule formulation. Patients with a confirmed diagnosis of cystic fibrosis who are 18 years of age or greater will be screened for eligibility if they have been clinically controlled on a stable dose of commercial pancreatic enzyme replacement therapy (PERT) for at least one month. Patients on cystic fibrosis transmembrane conductance regulator (CFTR) modulator therapies must have been on a stable dose for at least 3 months prior to study entry, and no dose changes will be made during the study. Patients receiving gastric acid suppressants must have been on a stable dose for at least one month prior to study entry and no dose changes will be made during the study. Upon obtaining an informed consent, potentially eligible patients will receive dietary counselling during the week prior to the scheduled date of confinement for collecting stool samples for calculation of baseline coefficient of fat absorption (CFA). This counselling will emphasize the importance of dietary stability during the study. Patients found to have a CFA of 80% or greater while receiving their commercial PERT and meeting the other eligibility criteria will be enrolled into the study.

Upon study enrolment, the patient will be switched from their commercial PERT to receive adrulipase. The patient will remain on study for approximately three weeks, after which a repeat CFA will be obtained. A dose titration scheme will be used for determining whether a low, medium, or high dose of adrulipase may succeed in controlling signs and symptoms of exocrine pancreatic insufficiency (EPI) and provide a CFA of 80% or greater. Patients will initially receive a low dose of adrulipase. Upon the appearance of EPI symptoms, lasting at least three days, and upon discussion with the investigator, the patient will be switched to the medium dose of adrulipase. If signs and symptoms of EPI persist for three or more days, the patient will be switched to the high dose of adrulipase. After patients reach 3 weeks of study and complete their end of study CFA, they will be returned to their pre-study commercial PERT. An end of study safety visit will be scheduled for one week after finishing adrulipase therapy.

Safety assessments will be made by collecting adverse events, safety lab assessments, and immunologic assays to assess drug induced immune responses.

3.3. Study Population

Subjects that are \geq 18 years of age with EPI due to CF and with CFA \geq 80% at screening while on stable PERT will be enrolled. The inclusion and exclusion criteria for the study are enumerated in Sections 8.3.2 and 8.3.3 of the protocol, respectively.

3.4. Sample Size

Based upon CFA data obtained in the recently completed Phase 2 studies (OPTION, OPTION 2), 12 patients using a dose titration scheme should provide sufficient point estimates of CFA and all other secondary efficacy endpoints. Given the acceptable safety profile obtained in the previous Phase 2 OPTION studies, a sample of 12 patients should be adequate for observation of safety.

4. GENERAL ANALYSIS AND REPORTING CONVENTIONS

The following is a list of general analysis and reporting conventions to be applied for this study.

Categorical variables will be summarized using counts (n) and percentages (%) and will be presented in the form “n (xx.x).” If a count is 0, 0% will be shown for the percentage. To ensure completeness, summaries for categorical and discrete variables will include all categories, even if no subjects had a response in a particular category.

Continuous variables will be summarized using mean, SD, minimum, maximum, median and number of subjects. The 25th and 75th percentiles will be provided for distributions that are known to be skewed. The mean, median, 25th percentile, 75th percentile, and confidence intervals (CI) will be reported to 1 more level of precision than the original observations, and the SD will be reported to 2 more levels of precision than the original observations. The minimum and maximum will be the same precision as the original data.

When p-values are provided, they will be rounded to 3 decimal places; p-values that round to “0.000” will be presented as “<0.001.” Unless otherwise stated, all statistical tests of treatment effects will be conducted at a 2-sided alpha level of 0.05.

All analysis will be performed using SAS® System version 9.4 or later.

Dates in listings will be displayed as yyyy-mm-dd (e.g., 2023-01-24).

The baseline value is defined as the last non- missing value on or before the first dose of study treatment.

Select displays will be presented by dose (1.2 g/day, 1.95 g/day, 2.4 g/day). Subjects will be classified by the maximum dose of adrulipase received during the study.

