11.5.2 Demographic and Other Baseline Characteristics

Demographic and other baseline characteristics will be summarized in the Safety Set:

- For each dose (i.e., 1.2 g/day, 1.95 g/day, 2.4 g/day, or 3.3 g/day)
- for all patients

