11.7 Efficacy Analysis

11.7.1 Primary Efficacy Endpoint

The primary efficacy endpoint is defined as the CFA assessed at the end of the approximately 21-day treatment period (Part 1) or 14-day treatment period (Part 2). CFA will be calculated as follows:

$$\text{CFA (\%)} = 100 \left(\frac{(\text{fat intake (g)} - \text{fat excretion (g)})}{\text{fat intake (g)}} \right)$$

Primary Analysis:

The primary analysis of the primary endpoint will be a comparison of the mean CFAs from the adrilipase treatment vs the PERT treatment (screening), using descriptive statistics. Data will be analyzed according to the protocol version under which patients enroll (ie, Part 1 [protocol version 1.0] or Part 2[protocol version 2.0]) according to the SAP.

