5.2. Per-Protocol Population

The per-protocol (PP) population is a subset of the mITT population and includes all mITT subjects without major protocol deviations that could impact the efficacy analyses. Protocol deviations will be captured throughout the study and classified as minor or major prior to database lock. Each major deviation will be categorized as either important or not important with respect to the effect on the primary endpoint analysis.

Subjects who are found to be <80% compliant with adrilipase will also be excluded from the PP population. The PP population will be used as supportive to the mITT population.

Prior to database lock, the protocol deviations will be reviewed and the PP Population will be determined.

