7.3. Measures of Treatment Compliance

Treatment compliance will be summarized in terms of g/day using a compliance rate and will be displayed overall and by maximum dose of adrulipase received during the study.

The compliance rate will be calculated as:

$$[\text{Actual Dose g/day} / \text{Expected Dose g/day}] * 100$$

The actual dose (g/day) a subject received will be calculated as:

$$[(\text{number pills dispensed} - \text{number of pills returned}) * 0.15 \text{ g}] / \text{number of actual study days on adrulipase},$$

where the number of actual study days on adrulipase is calculated as:

$$(\text{date/time of last adrulipase dose} - \text{date/time of first adrulipase dose}) / 86400 + 1.$$

The expected dose for adrulipase depends on whether the subject titrated to a higher dose during the study, e.g. low dose (1.2 g/day), medium dose (1.95 g/day), high dose (2.4 g/day), and is calculated as:

$$1.2 \text{ g}/(\text{days on low dose}) + 1.95 \text{ g}/(\text{days on medium dose}) + 2.4 \text{ g} (\text{days on high dose})$$

First Wave BioPharma, Inc.
{Statistical Analysis Plan - Protocol #} FWB-CF-2.03

Treatment compliance will be summarized using descriptive statistics.

As described in Section [5.2](#), subjects found to be <80% compliant with adrulipase will be excluded from the PP population.

Individual data for study drug (number of capsules) dispensed and returned, and treatment compliance will be listed for subjects in the mITT population. a

Note that since capsules are dispensed at one visit and returned at one visit (e.g. not separately b

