9.2. Primary Endpoint

The primary endpoint analyses will be presented overall and by dose. Subjects are classified by maximum dose of adrlipase received during the study.

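### The SAP predates Part 2: it has no by-Part analysis and no 3.3 g/day level, and its expected-dose formula breaks the 80% per-protocol rule in both Parts

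*SAP*

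**What the plan says.** SAP section 2 says the plan was developed after review of "protocol number FWB-CF-2.03 (Version 1.0), but before any analyses of the data". It adds: "If differences occur between analyses described in the SAP and the current protocol, those found in this SAP will assume primacy". The design it describes is the Part 1 design only, with titration through three doses over three weeks. Section 4 states "Select displays will be presented by dose (1.2 g/day, 1.95 g/day, 2.4 g/day" and classifies patients by the highest dose received. The same three levels recur in SAP 3.1.1, 6.2, 7.3 and 8.2. For CFA, SAP 9.2 says: "The primary endpoint analyses will be presented overall and by dose".

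The current protocol has two Parts. Part 1 is the titrated three-week design. Part 2 gives every patient 3.3 g/day for two weeks without titration (protocol 8.1, 8.1.1, 8.4.2). Protocol 11.7.1 says "Data will be analyzed according to the protocol version under which patients enroll", names the two Parts, and refers to the SAP for the method. Protocol 11.5.2 lists the dose groups: "For each dose (i.e., 1.2 g/day, 1.95 g/day, 2.4 g/day, or 3.3 g/day".

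SAP 7.3 defines compliance as actual g/day over expected g/day, times 100. Writing dL, dM and dH for days on the low, medium and high dose, the printed expected dose is `1.2/dL + 1.95/dM + 2.4 × dH`. SAP 5.2 then uses the result: "Subjects who are found to be <80% compliant with adrilipase will also be excluded from the PP population".

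SAP 8.5, 8.6.1, 9.2.1, 9.2.2, 9.3.2 and 9.3.3 name time points as one, two or three weeks after first dose or as the end of a three-week period. SAP 9.2.2 and 9.2.4 place the CFA responder summary at week 6.

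**The concern.** The protocol hands the by-Part primary analysis to a document that does not contain it. Part 2 patients have no column in any listed by-dose display, yet they enter the overall CFA row. That row averages patients titrated over about three weeks with patients on a fixed, higher dose for about two. The study is descriptive, so these summaries are its result.

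The compliance formula decides who is in the per-protocol set, which supports the primary endpoint. It has no Part 2 term. In Part 1 it divides by days for two doses, multiplies by days for the third, and never divides by total days, so it does not give g/day. Followed literally, it would remove adherent patients who reached the high dose and keep almost anyone who did not.

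The time labels do not fit Part 2, where Visits 4, 5 and 6 fall on Days 3, 7 and 10 (protocol Table 2). The week 6 label also disagrees with the schedules, which put Visit 6 in study week 4. This is a labelling fault only, because the Visit 6 data can be identified.

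**Working it through.** **Doses from the capsule schedule (protocol 8.4.1, 150 mg capsules, three meals and two snacks).**
- Low: 3×2 + 2×1 = 8 capsules, 8 × 0.15 = 1.2 g/day.
- Medium: 3×3 + 2×2 = 13, giving 1.95 g/day.
- High: 3×4 + 2×2 = 16, giving 2.4 g/day.
- Part 2: 3×6 + 2×2 = 22, giving 3.3 g/day.

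All four agree with the protocol. The documents give no worked compliance value to reproduce, so the test is whether a fully adherent patient scores 100%.

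**Part 1, high dose reached, formula as printed.** Assume 5, 5 and 11 days on low, medium and high.
- Actual: (1.2×5 + 1.95×5 + 2.4×11)/21 = 42.15/21 = 2.007 g/day.
- Printed expected: 1.2/5 + 1.95/5 + 2.4×11 = 0.24 + 0.39 + 26.4 = 27.03.
- Compliance: 2.007/27.03 = 7.4%.

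**Range.** Assume 16 to 28 days in total, at least 3 days each on low and medium, and at least 1 on high. That gives 1,859 whole-day splits.
- Lowest, 3/3/22 days: (62.25/28)/(0.40 + 0.65 + 52.8) = 2.223/53.85 = 4.1%.
- Highest, 5/22/1 days: (51.3/28)/(0.240 + 0.089 + 2.4) = 1.832/2.729 = 67.1%.

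No split reaches 80%. A bound that needs no such assumption: the daily average of an adherent Part 1 patient cannot exceed 2.4 g. With two or more days on the high dose, the printed expected dose is at least 4.8, so compliance is at most 50%.

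**Part 1, high dose not reached.**
- Low plus medium, 10/11 days: actual 33.45/21 = 1.593; expected 1.2/10 + 1.95/11 = 0.297; compliance 536%. A patient who took half the capsules would still read 268%.
- Same limits on total days, at least 3 on each dose: 181% to 740%.
- Low dose only: the medium term is 1.95/0, so the formula is undefined.

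**Could a misprinted slash explain it?** No alternative reading returns 100%.
- All terms divided, 5/5/11: 0.24 + 0.39 + 2.4/11 = 0.848; 2.007/0.848 = 236.6%. The adherence needed to pass is 0.80 × 0.848/2.007 = 33.8%.
- All terms multiplied: the result is total grams, so compliance is 100/days, or 4.8% at 21 days.

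**Part 2.** Days on all three listed doses are zero, so the expected dose is undefined. If 2.4 g/day were borrowed as the denominator, full adherence would read 3.3/2.4 = 137.5%, and a patient taking 0.80 × 2.4/3.3 = 58% of capsules would pass.

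**Day-weighted replacement.** `(1.2·dL + 1.95·dM + 2.4·dH + 3.3·dP2) / total days`, where dP2 is days on treatment in Part 2. Every fully adherent patient scores 100%. In Part 2 the 80% cut is 0.80 × 3.3 = 2.64 g/day, or 2.64/0.15 = 17.6 of 22 capsules.

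**The case against.** The strongest reply is that the intent is clear. SAP 7.3 calls the quantity g/day, so a programmer would use a day-weighted mean, and 3.3 g/day is the obvious expected dose for a fixed-dose group. Adherent patients reading about 7% would be noticed when the per-protocol set is reviewed before lock. The text of SAP 7.3 available here also breaks off mid-sentence in a note on capsule dispensing and return, so some compliance wording may be unseen.

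Further, the primacy clause applies where the documents differ, and a display by dose does not contradict one by Part. Since only Part 2 uses 3.3 g/day, adding that level would isolate Part 2 under the maximum-dose rule. The SAP is dated 2023-04-13 and built on Version 1.0, so a later SAP may exist. The per-protocol set is supportive, and no test, alpha or power is involved.

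Much of this limits the consequence. It is fair that the primacy clause alone does not exclude a by-Part display, and the point applies only to the SAP supplied. The labels are editorial, and protocol Table 2 is itself loose in pairing study week 4 with Day 10. But a rule that decides membership of an analysis set should not rely on silent repair: the printed formula is wrong under every reading tried, and the 3.3 g/day term is absent. Adding 3.3 g/day to the dose lists would still leave no combined Part 1 summary and an overall row that pools the Parts.

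**Conclusion.** The concern holds for the SAP supplied and should be corrected before database lock. The by-Part primary presentation that the protocol requires is missing, and the only listed row containing Part 2 patients is a pooled one.

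The 80% compliance criterion cannot be applied as written in Part 2; the major-deviation criterion still can. In Part 1 it errs in both directions. Protocol 6.7 reports that five of the six patients enrolled when Version 2.0 was written had been dosed at 2.4 g/day. Under the day-split assumptions stated above, all five would fail the printed rule even with perfect adherence, while patients staying on lower doses could hardly fail it.

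The exact percentages depend on the assumed day splits; the conclusion that the formula is wrong does not. The mITT CFA summary is unaffected by the compliance error.

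**What to change.** Amend the SAP to protocol Version 2.0 before database lock:

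1. Make CFA by Part the main summary, and do the same for CNA, which protocol 11.7.2 says is analysed like CFA. Label any pooled overall row as supplementary. Add 3.3 g/day to the dose lists in SAP 3.1.1, 4, 6.2, 7.3 and 8.2.
2. Replace the expected dose with the day-weighted formula above, and apply the 80% rule to actual over expected in both Parts. Take days at each level from the first and last dose dates that SAP 8.2 already lists, and use one count of total days for both actual and expected dose.
3. Name time points by visit number: CFA and the CFA responder summary at Visit 6, symptoms after first dose at Visits 4, 5 and 6.
4. Update the protocol version cited in SAP section 2, so that the primacy clause rests on the current design. This adds little once items 1 to 3 are in place.

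The cost is a SAP amendment, revised table shells and one formula. No new data are needed. The drawback is fewer patients per column than in the pooled row, out of about 12 planned.
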